3.2.4 Safety

Objective(s)	Endpoint(s)
• To evaluate the safety and tolerability of cenegegermin vs. vehicle, as measured by Treatment-Emergent Adverse Events (TEAEs).	• Incidence and frequency of TEAEs, assessed throughout the study.

3.3 Schedule of evaluations

[figure not shown]
During the screening (day-8) all procedures for inclusion will be performed. From the day of screening the patients will stop any kind of further treatment, except commercially available preservative free artificial tears provided by Sponsor for a period of 8 days and 10 days as maximum: day -8 until the baseline visit (day 1+2). At the end of the wash out period (day -8 to baseline), patients meeting the entry criteria for this study will be randomized 1:1 and treated for 4 weeks with either cenegegermin ophthalmic solution 20 mcg/mL TID or vehicle TID.

During the 4 weeks of masked treatment only the administration of the Investigational Medicinal Product (IMP) is allowed. Nevertheless, if strictly needed, the patient can take preservative free artificial tears (provided by the Sponsor). The use (n° drops/day) of preservative free artificial tears will be clearly documented in a patient's diary and in the eCRF.

Eight weeks post treatment with no further topical ocular treatment except commercially available preservative-free artificial tears provided by the Sponsor three times daily will follow the completion of the double-blind treatment. During this follow-up period, the patient can administer additional artificial tear eye drops, provided by Sponsor, only if strictly needed, and must document in the patient's diary the number of additional drops administered for each eye.

Patients will then be followed-up for efficacy and safety endpoints until week 16 and for safety endpoints until week 24. During the follow-up period after week 12 until week 24 other topical treatments will be allowed at discretion of the treating physician. Such treatments will be recorded by the investigators.

Throughout the study, the patient can continue any systemic treatment as required to control their autoimmune disease, and any change in systemic treatments must be recorded by the investigators.

Figure 1: Study duration

4. General definitions

4.1 Investigational drug and study treatment

Oxervate®, an ophthalmic solution containing cenegegermin 20 mcg/mL, which is a recombinant human Nerve Growth Factor (rhNGF); reference product is vehicle. Test and reference will be instilled in both eyes according to the following scheme:

- Group 1: one drop of cenegegermin 20 mcg/mL will be instilled in both eyes three times daily (every 6 hours, e.g. 7:00 am, 02:00 pm; 09:00 pm).
- Group 2: vehicle eye one drop will be instilled in both eyes three times daily (every 6 hours, e.g. 7:00 am, 02:00 pm; 09:00 pm).

The IMP will be provided in a monthly box containing 28 daily vials. Together with the IMP monthly box, patients will be provided with enough pipettes and adaptors for the administration of the IMP.

4.2 Date of first and last administration of study drug

The date of first administration of study drug is defined as the date of first administration of IMP as per IMP Administration eCRF form (information transcribed from Patient Diary).

The date/time of last administration of study drug is defined as the Date of last treatment administration as per End of treatment eCRF form. This value has to be consistent with IMP Administration information recorded on the corresponding eCRF forms. In case of different dates, the latest will be used as treatment end.

4.3 Study day

The study day describes the day of the event or assessment date, relative to the reference start date which is the date of Visit 1 - Baseline.

The study day is defined as:

- The date of the event (visit date, onset date of an event, assessment date etc.) – reference start date + 1 if event is on or after the reference start date.
- The date of the event (visit date, onset date of an event, assessment date etc.) – reference start date if event precedes the reference start date.

4.4 Visit Schedule and Visit Windows

Assessments and study visits will be performed as listed in Paragraph no. 2 (“Schedule of evaluations”) and in Paragraphs no. 6 (“Study Procedure and Assessments”) of the Study Protocol [1] containing additional details about scheduled visits and time windows.

Scheduled visits and time windows are:

- Screening (Day -8)
- Visit 1 - Baseline (Day 1 + 2 days)
- Visit 2 - Week 2 (Day 14 ± 2 days)
- Visit 3 - End of treatment Week 4 (Day 28 ± 2 days)
- Visit 4 - follow-up Week 8 (Day 56 ± 2 days)
- Visit 5 - follow-up Week 12 (Day 84 ± 4 days)
- Visit 6 - follow-up Week 16 (Day 112 ± 7 days)
- Visit 7 - follow-up Week 24 (Day 168 ± 7 days)

For efficacy and safety endpoints, data will be evaluated according to the Visit at which they have been collected.

4.5 Baseline

Baseline is defined as the last visit prior to and including date of the randomization visit (Visit 1). Unless otherwise specified, baseline values are defined as the measurements taken during this visit. In case of multiple measurements during baseline visit, the last assessment will be considered as baseline evaluation before start of treatment.

4.6 Post-baseline

For safety and efficacy evaluations all assessments after the first administration of study drug are considered as “post-baseline” assessment.

4.7 Eligible eye

Assuming that all the inclusion/exclusion criteria are met in both eyes, the worse eye (eligible eye) will be determined at the baseline visit using a stepladder approach, as follows:

1. Schirmer’s Test: worse eye determined as eye with lower Schirmer I score.
2. NEI score: if Schirmer I score is the same in both eyes, worse eye will be determined by NEI score (cornea + conjunctival staining).

If all the above are identical, determination of the worse eye will be based on the investigator’s judgement, otherwise the right eye will be used as the eligible eye.

5. Sample size justification

The sample size of the study is calculated based on results from previous studies.

Sample size was calculated according to the following assumptions:

- randomization ratio 1:1.
- a difference of 30% in Schirmer I rate of responders (value >10mm/5min at week 4.) in favor of rhNGF treatment at Week 4, with a responder rate of 5% for vehicle.
- 15 points in Global SANDE score improvement at Week 12, with a standard deviation of 20 points.

Based on these assumptions, a total sample size of 90 evaluable patients (100 pts considering 10% of patients not evaluable after enrollment) allows to achieve an overall power of 90% to show superiority of rhNGF eye drops solution vs vehicle in terms of both co-primary endpoints, considering a one-sided alpha of 0.025. Specifically:

- A power of 95.8% is achieved for Schirmer I primary endpoint.
- A power of 94.0% is achieved for SANDE primary endpoint.

6. Randomization and blinding

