7.3 Primary estimand

The primary endpoints will be analyzed using treatment policy estimands, defined by the following:

Primary endpoint:

- Population: Subjects in the FAS population.
- Variable: Schirmer I test at week 4.
- Intercurrent event: The occurrence of an intercurrent event is irrelevant. All observed values will be used regardless of occurrence of an intercurrent event. Retrieved dropouts will be used for data imputation of missing data.
- Population-level summary: difference in proportion of patients reaching a value of Schirmer I test (without anesthesia) >10mm/5min at week 4.

Coprimary endpoint:

- Population: Subjects in the FAS population.
- Variable: SANDE global score at week 12.
- Intercurrent event: The occurrence of an intercurrent event is irrelevant. All observed values will be used regardless of occurrence of an intercurrent event. Retrieved dropouts will be used for data imputation of missing data.
- Population-level summary: difference in change from baseline in the global SANDE score at week 12.

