10.1.2 Analysis details

Both co-primary endpoints will be analysed by means of MI-RD to handle missing data. Retrieved drop-out patients are defined as patients who discontinue study treatment and decide to remain in the study by following the schedule of assessments and continuing to adhere to protocol requirements. Consequently, for each primary endpoint, MI will be performed based on the subjects' allocated treatment arm and observed values (baseline and intermediate) as covariates in a regression model using data from Retrieved drop-out patients that have the primary endpoint assessment done.

10.1.2.1 Schirmer I test $>10\text{mm}/5\text{min}$ at week 4

This primary endpoint will be analyzed by means of a logistic regression model adjusting by pre-defined baseline factors (gender, age class, baseline Schirmer I test value as fixed effects and site as random effect) and a one-sided test will be used to test for differences between treatment groups.

For the imputation of missing data of Schirmer I test, a regression model will be created by including the baseline Schirmer I test value, gender, age class, and Schirmer I test at week 2. Two hundred data sets will be generated, and the random seed number will be 820520. MI will be implemented in the following steps:

1. Partial imputation assuming Missing at Random (MAR) will be carried out to impute intermittent (non-monotone) missing data of Schirmer I test up to week 4 based on a

multivariate joint Gaussian imputation model using the Markov chain Monte Carlo (MCMC) method. A separate imputation model will be used for each treatment arm. In case of non-convergence or non-estimability issues, a single imputation model will be considered (with treatment arm added as explanatory variable to the model). A total of 200 datasets will be created. These datasets will be utilized in Step #2.

2. The remaining monotone missing data will be imputed using a MI regression including the same explanatory variables of the previous step. According to MI-RD approach, only non-missing values from retrieve dropouts will be used to inform the regression model.
3. Each of the 200 imputed datasets will be analyzed using observed and imputed data. Rubin's rule will be used for combining results to draw inference.

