10.2.2.1 Schirmer I test >10mm/5min at week 8

The proportion of patients reaching a value of Schirmer I test (without anesthesia) >10mm/5min at week 8 will be analyzed as described in section 10.1.2.1 for the primary efficacy endpoints.

10.2.2.2 Change from baseline in SANDE score for severity at week 12

The change from baseline in SANDE score for severity at week 12 will be analyzed as described in section 10.1.2.2 for the primary efficacy endpoints.

10.2.2.3 Change from baseline in SANDE scores for frequency at week 12

The change from baseline in SANDE score for frequency at week 12 will be analyzed as described in section 10.1.2.2 for the primary efficacy endpoints.

10.2.2.4 Change from baseline in IDEEL modules (Quality of Life, Dry eye Treatment satisfaction & Bother, and Dry eye Symptom bother) at week 12 and at week 4

Rules for derivation of IDEEL scores are reported in section 12.3. The change from baseline of each IDEEL module will be analyzed by means of an MMRM adjusting by pre-defined factors (gender, age class, IDEEL module baseline value, treatment, visit, and treatment by visit interaction; subject will be considered as a random effect). The covariance matrix used will be "unstructured". Comparisons versus vehicle TID will be provided using least square means at each visit and overall and a one-sided test will be used to test for differences between treatment groups.

For the imputation of missing data, a regression model will be created by including the baseline value, gender, age class, and intermediate scores up to week 12. Two hundred data sets will be

generated, and the random seed number will be 225670. MI will be implemented in the following steps:

1. Partial imputation assuming MAR will be carried out to impute intermittent (non-monotone) missing data of IDEEL module score based on a multivariate joint Gaussian imputation model using the MCMC method. A separate imputation model will be used for each treatment arm. In case of non-convergence or non-estimability issues, a single imputation model will be considered (with treatment arm added as explanatory variable to the model). A total of 200 datasets will be created. These datasets will be utilized in Step #2.
2. The remaining monotone missing data will be imputed using a MI regression including the same explanatory variables of the previous step. According to MI-RD approach, only non-missing values from retrieve dropouts will be used to inform the regression model.

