15.5 SAS Code for the primary analysis

15.5.1 Schirmer I test >10mm/5min at week 4

Standard	Alternative code in case of no convergence
<pre> PROC MI DATA= EFFICACY01 NIMPUTE=200 SEED=820520 OUT=EFFICACY_MONO1; VAR BASVAL SCHIRMER_W2 AVAL; MCMC CHAIN=SINGLE NBITER=200 NITER=100 IMPUTE=MONOTONE; WHERE TRT=1; RUN; PROC MI DATA=EFFICACY01 NIMPUTE=200 SEED=820520 OUT=EFFICACY_MONO2; VAR BASVAL SCHIRMER_W2 AVAL; MCMC CHAIN=SINGLE NBITER=200 NITER=100 IMPUTE=MONOTONE; WHERE TRT=2; RUN; DATA EFFICACY_MONO; SET EFFICACY_MONO1 EFFICACY_MONO2; RUN; </pre>	<pre> PROC MI DATA= EFFICACY01 NIMPUTE=200 SEED=820520 OUT=EFFICACY_MONO; VAR BASVAL TRT SCHIRMER_W2 AVAL; MCMC CHAIN=SINGLE NBITER=200 NITER=100 IMPUTE=MONOTONE; RUN; </pre>
<pre> PROC SORT; BY _IMPUTATION_ SUBJID; RUN; </pre>	
<pre> PROC MI DATA=EFFICACY_MONO SEED=200582 NIMPUTE=1 OUT=EFFICACY_IMP; BY _IMPUTATION_; CLASS TRT AGE SEX EOTSTT; MONOTONE REG(AVAL = TRT AGE SEX BASVAL / DETAILS); MNAR MODEL(AVAL / MODELOBS= (EOTSTT='NOT COMPLETED')); VAR TRT AGE SEX BASVAL SCHIRMER_W2 AVAL; RUN; </pre>	<pre> PROC MI DATA=EFFICACY_MONO SEED=200582 NIMPUTE=1 OUT=EFFICACY_IMP; BY _IMPUTATION_; CLASS TRT AGE SEX EOTSTT; MONOTONE REG(AVAL = TRT AGE SEX BASVAL / DETAILS); MNAR MODEL(AVAL / MODELOBS= (TRT=2 /*Vehicle*/)); VAR TRT AGE SEX BASVAL SCHIRMER_W2 AVAL; RUN; </pre>

Standard	Alternative code in case of no convergence
<pre> DATA EFFICACY_IMP; SET EFFICACY_IMP; IF AVAL>10 THEN AVALC='Y'; ELSE AVALC='N'; RUN; ODS OUTPUT DIFFS=GLIMMIX_DIFFS; ODS OUTPUT PARAMETERESTIMATES=ESTIMATES; PROC GLIMMIX DATA=EFFICACY_IMP METHOD = QUAD; BY _IMPUTATION_; CLASS TRT(REF="1") AGE(REF="<=XX") SEX(REF="F") SITEID; MODEL AVALC(EVENT='Y')=TRT AGE SEX BASVAL /S DIST=BINARY LINK=LOGIT OR; RANDOM INTERCEPT / SUBJECT=SITEID; LSMEANS TRT / ILINK ODDSRATIO CL DIFF; RUN; ODS OUTPUT PARAMETERESTIMATES=POOLED_ESTIMATES; PROC MIANALYZE PARMS = ESTIMATES ; CLASS TRT AGE SEX; MODELEFFECTS INTERCEPT TRT AGE SEX BASVAL ; RUN; ODS OUTPUT PARAMETERESTIMATES=POOLED_DIFFS; PROC MIANALYZE DATA = GLIMMIX_DIFFS ; MODELEFFECTS ESTIMATE; STDERR STDERR; RUN; DATA POOLED_ODDS_RATIO; SET POOLED_DIFFS; ODDSRATIO=EXP(ESTIMATE); ODDS_95LL=EXP(LCLMEAN); ODDS_95UL=EXP(UCLMEAN); RUN; </pre>	

15.5.2 Change from baseline in the global SANDE score at week 12

Standard	Alternative code in case of no convergence

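### The stated 95.8% Schirmer power (90% overall) belongs to a different test: the planned Wald logistic test cannot reject if no vehicle patient responds, so its power is about 87% (about 82% overall)

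*SAP*

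**What the plan says.** SAP Section 5 sets the Schirmer assumptions as a 30-point difference "in favor of rhNGF treatment at Week 4, with a responder rate of 5% for vehicle", 1:1 allocation and 90 evaluable patients out of 100, "considering a one-sided alpha of 0.025". It then states "A power of 95.8% is achieved for Schirmer I primary endpoint", with 94.0% for SANDE and 90% overall. It does not name the test behind these figures. Protocol 9.1 repeats the 90% without giving a vehicle rate.

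On the analysis, SAP 10.1.2.1 says: "This primary endpoint will be analyzed by means of a logistic regression model adjusting by pre-defined baseline factors", with gender, age class and baseline Schirmer as fixed effects and site as a random effect. The code in SAP 15.5.1 fits PROC GLIMMIX by quadrature in each of 200 imputed datasets and pools the log-odds difference with its standard error: "PROC MIANALYZE DATA = GLIMMIX_DIFFS ; MODELEFFECTS ESTIMATE; STDERR STDERR; RUN". The result is then exponentiated: "ODDSRATIO=EXP(ESTIMATE". The code column offered for non-convergence changes only the imputation steps.

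SAP 7.3 defines the target differently: "Population-level summary: difference in proportion of patients reaching a value of Schirmer I test (without anesthesia) >10mm/5min at week 4". SAP 10.2.2.1 applies the same model to the first key secondary, where responders at "week 8 will be analyzed as described in section 10.1.2.1 for the primary efficacy endpoints". SAP 10.1.1 requires both co-primary nulls to be rejected.

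**The concern.** A pooled estimate divided by its pooled standard error is a Wald test, although the SAP does not use the word. The plan expects 45 × 0.05 = 2.25 vehicle responders, so a count of zero is quite possible. With zero, the data are separated: the maximum-likelihood log-odds ratio is infinite and its standard error grows faster than the estimate. The test statistic then falls to about zero just when the contrast between arms is greatest.

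The stated overall power has no slack, since 0.958 × 0.940 = 0.9005. A failed Schirmer test fails the trial and closes the key secondary sequence. If separation appeared after unblinding, the sponsor would have to accept a meaningless p-value or choose another primary test post hoc.

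**Working it through.** **Inputs.** From SAP Section 5: 5% vs 35%, 45 evaluable per arm, one-sided 0.025, SANDE difference 15 with SD 20. From SAP 15.5.1: the test statistic is the log-odds difference divided by its standard error.

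**1. Reproduce the stated power.** Pooled-variance z-test with mean rate 0.20:
- SE under the null = √(0.20 × 0.80 × 2/45) = 0.0843
- SE under the alternative = √((0.05 × 0.95 + 0.35 × 0.65)/45) = 0.0782
- Power = Φ((0.30 − 1.96 × 0.0843)/0.0782) = Φ(1.72) = 0.9576, the stated 95.8%

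The two-sample t-test for SANDE (d = 15/20 = 0.75, 88 df) gives 0.9404, the stated 94.0%. The product is 0.9005, the stated 90%. The arithmetic is right, but for a test that is not planned.

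**2. Chance of zero vehicle responders.** 0.95^45 = 0.0994. With 50 per arm, 0.95^50 = 0.0769.

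**3. Exact power of the Wald test.** Let a and b be the vehicle and cenegermin responder counts, with n = 45. Reject when

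ln[b(n − a)/(a(n − b))] / √(1/a + 1/b + 1/(n − a) + 1/(n − b)) > 1.96.

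With a = 1, 2, 3 or 4, rejection needs b of at least 8, 9, 10 or 12. With a = 0 there is no rejection at any b. Summing Binomial(45, 0.05) × Binomial(45, 0.35) over the rejection region gives **0.8674**. Given at least one vehicle responder, power is 0.8674/(1 − 0.0994) = 0.963, so the zero-responder case explains essentially the whole loss.

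Simulations adjusting for age class, sex and baseline gave 85.6% to 87.5%. In the runs that tracked it, no trial with zero vehicle responders rejected.

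**4. An example.** For 0/45 vs 16/45, a logistic fit gave an estimate of about 20 with a standard error of about 2,200, so one-sided p is about 0.50. Fisher's exact p is 3 × 10⁻⁶. The fitted values depend on where the algorithm stops, but the ratio stays near zero.

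**5. Overall power, assuming independent endpoints as the SAP does.** 0.867 × 0.940 = 0.815, or 0.820 with a z-based SANDE power. Even under perfect dependence it cannot exceed 86.7% with 45 per arm.

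**6. Other tests, same assumptions, unadjusted, 45 per arm.**

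| Test | Schirmer power |
|---|---|
| Wald logistic (as planned) | 86.7% |
| Fisher exact | 94.7% |
| Wald with 0.5 added to each cell (Firth-type) | 96.0% |
| Likelihood ratio or Pearson | 97.5% |

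The Wald test would need about 65 evaluable patients per arm (96.1%) to reach the stated figure.

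**7. Dependence on the vehicle rate, keeping a 30-point difference, 45 per arm.**

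| Vehicle rate | P(zero responders) | Pooled z power | Wald power |
|---|---|---|---|
| 3% | 25.4% | 97.1% | 72.7% |
| 5% | 9.9% | 95.8% | 86.7% |
| 8% | 2.3% | 93.6% | 92.0% |
| 10% | 0.9% | 92.1% | 91.8% |

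**8. Multiple imputation.** Rubin's rules average the within-imputation variances. One separated dataset out of 200 with SE 2,200 adds 2,200²/200 = 24,200 to the variance, so the pooled SE is at least √24,200 = 156. Even if all 200 estimates were 20, the statistic would be only 20/156 = 0.13. As an illustration, suppose no vehicle response is observed, five vehicle values are missing, and each has a 20% chance of being imputed above 10 mm. The chance that all 200 datasets contain a responder is (1 − 0.8⁵)^200, about 3 × 10⁻³⁵. If separated fits failed and dropped out instead, the primary result would rest on an unplanned subset.

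**The case against.** **Evaluable numbers.** The primary analysis uses the FAS, about 50 per arm, and week-4 data may be more complete than the overall 10% loss implies. With 50 complete patients per arm, Wald power is 90.3%. Overall power is 0.903 × 0.940 = 0.849 with SANDE held at 94.0%, or about 87% with SANDE also at 50 per arm. This is fair as the upper end of a range, but still short of 95.8% and 90%.

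**Vehicle rate.** The gap nearly closes at 8% to 10%. That is true, but 5% is the plan's own assumption.

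**Power of the remedy.** The 96.0% comes from an unadjusted table with 0.5 added. Simulated Firth models with covariates gave 95.3% and 96.3% without site and 95.6% with pooled sites. With ten fixed sites they gave 95.1% when sites were balanced by arm, and 93.4% in another simulation. So 96% and 90% are right to within about a point for pooled sites, but ten separate site effects could cost more.

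**Random site effect.** Dropping it changes the SAP model. However, Protocol 9.4.3.1 lists site only as an adjustment factor, so a pooled or fixed site term is consistent with the protocol.

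**Full procedure.** The random intercept and the imputation were not simulated, so the exact percentages are less certain than the separation problem itself.

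**Severity.** Nothing here favours the drug: the Wald test's one-sided error is about 0.0005 when both rates are 5%. The defect is lost power and a decision rule that breaks down, not a false-positive risk.

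**Week 8.** No week-8 vehicle rate is given, so the weakness there is real but cannot be sized.

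**Estimand.** SAP 10.1.2.1 promises adjusted differences in proportions, and the code requests arm-level probabilities through ILINK. The gap is that the code neither pools that difference nor gives it a confidence interval.

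**Conclusion.** The concern holds. The 95.8% is correct for a pooled two-proportion z-test but is not the power of the planned analysis. At the SAP's own assumptions and 45 evaluable patients per arm, the unadjusted form of the planned Wald test has 86.7% power, about 82% overall. With 50 complete patients per arm the figures are 90.3% and 85% to 87%. These rest on a 5% vehicle rate, a 35% cenegermin rate and independent endpoints. The loss comes almost wholly from a 9.9% chance of zero vehicle responders, for which the plan has no rule. The first key secondary inherits the same weakness. The missing pooled difference in proportions is a separate, smaller mismatch with the estimand. Because a co-primary decision rule is affected, this must be settled before unblinding.

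**What to change.** 1. **At minimum**, restate the power in SAP Section 5 for the test specified: about 87% for Schirmer and 82% overall with 45 per arm, with the 50-per-arm figures alongside.
2. **Better**, pre-specify Firth-penalised logistic regression for responders at weeks 4 and 8, adjusted for gender, age class, baseline Schirmer and site, with estimates and standard errors pooled by Rubin's rules. Pool sites by a rule fixed at the blind data review. The 0.5-added version kept one-sided type I error below 0.025 at common rates of 5%, 10% and 20%. Quote the power of the adjusted model: the simulated 95.6% with pooled sites gives 0.956 × 0.940 = 0.899 overall.
3. **For the estimand**, compute the model-standardised difference in proportions and its standard error in each imputed dataset, pool them, and report the 95% confidence interval.

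The cost is SAP wording, a few lines of code, and replacing the random site intercept with a pooled or fixed site term. No extra patients are needed.
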